6.4.8 SARS-CoV-2 TESTING

Phase 2 segment:

SARS-CoV-2 antibody and RT-PCR testing will be used during screening to test for previous or current SARS-CoV-2 infection. During the trial, subjects who report symptoms suggestive of COVID-19 will be assessed at a COVID-19 assessment visit in the clinic or subject's vehicle or at the subject's home. During this visit, nasal swabs and saliva will be collected to detect SARS-CoV-2 using the RT-PCR assay. Genotyping may also be performed. If the subject is confirmed to be COVID-19 positive, a follow-up nasal swab and saliva will be collected to detect SARS-CoV-2 using the RT-PCR assay at the COVID-19 convalescent visit.

Phase 3 segment:

SARS-CoV-2 antibody testing will be used during screening to test for previous SARS-CoV-2 infection and during each subsequent visit (see Table 4: Schedule of Events) to identify SARS-CoV-2 infections that may occur regardless of symptoms between study visits.

SARS-CoV-2 RT-PCR testing will be conducted on nasopharyngeal specimens collected at Day 0. The Day 0 SARS-CoV-2 RT-PCR results will not be required prior to dosing on that day.

For subjects who are seronegative at baseline, if at any time during the trial, either the SARS-CoV-2 antibody or an RT-PCR test result is positive, the subject will be notified of the result and will be evaluated at a COVID-19 assessment visit. During that visit, which may be conducted in the clinic, from the subject's vehicle, or in the subject's home, nasopharyngeal swabs will be collected to detect SARS-CoV-2 using the RT-PCR assay. Genotyping may also be performed on the sample(s) collected at the COVID-19 assessment visit.

6.4.9 COVID-19 DISEASE MONITORING

During both the Phase 2 and Phase 3 segments of the trial, all subjects will be monitored for the development of symptoms suggestive of COVID-19 disease. For the Phase 3 segment, frequent (approximately bi-weekly) scheduled clinic visits or phone calls will occur.

All subjects in the trial should be instructed to do the following:

- Take their temperature daily at home starting on the Day 0 visit for the duration of the trial.
- Monitor for symptoms suggestive of COVID-19 (e.g., feeling feverish or chills, cough, shortness of breath or difficulty breathing, fatigue, muscle or body aches,

INO-4800	COVID19-311
Inovio Pharmaceuticals, Inc.	Clinical Protocol

headache, new loss of taste or smell, sore throat, congestion or runny nose, nausea or vomiting, diarrhea) starting on the Day 0 visit for the duration of the trial.

If at any time during the study, the subject experiences a fever of $\geq 100.4^{\circ}F/38^{\circ}C$ or symptoms suggestive of COVID-19, the subject should contact the site. The site staff should arrange for a clinic visit (COVID-19 assessment visit) within 3 days of the site being aware of either a positive SARS-CoV-2 test or COVID-19 symptom onset. The COVID-19 assessment visit may be performed either at the clinic, in the subject's vehicle or in the subject's home.

Subjects with a confirmed COVID-19 diagnosis, per the case definition outlined in Section 3.7, prior to dose 2 or who have a positive SARS-CoV-2 PCR test at Day 0 will be discontinued from further dosing and will be followed until EOS for safety and resolution of COVID-19. Subjects with confirmed SARS-CoV-2 infection will return for a convalescent visit approximately 28 days after symptom onset, or in the absence of symptoms, after the collection date of the positive SARS-CoV-2 sample. If symptoms are ongoing at 28 days after symptom onset, the site should follow up with the subject via phone call or unscheduled visit after symptom resolution or stabilization. Recovery from COVID-19 disease requires either resolution of clinical symptoms except for loss of taste/smell, or with sequelae that appear to be permanent.

Subjects who require medical care for COVID-19 (or any other suspected condition) will be referred to their primary health care provider or a medical treatment facility if the Investigator believes that the subject should be managed beyond routine care that can be provided by the study site. Subjects referred for treatment will continue study follow-up according to the protocol schedule. If subjects are treated or hospitalized due to their illness, the study team will request COVID-19 specific test results, treatments, treatment outcomes and diagnostics from medical treatment facilities with the subject's written permission. These results and diagnostics will be recorded in the study and/or safety database consistent with protocol reporting requirements.

6.5 **IMMUNOGENICITY ASSESSMENTS**

Whole blood and serum samples will be obtained at visits specified in the Schedule of Events (Tables 3 and 4) for cellular and humoral immunology assessments. Binding ELISA will be evaluated at serial timepoints. Cellular sampling requires 32 mL of whole blood be collected at each visit. Humoral sampling requires collection of 8.5 mL of whole blood in a single 10-mL red top serum collection tube to produce two serum aliquots of 2 mL each. However, baseline (Day 0) immunology samples are required to serve as a baseline for all subsequent immunology testing. Therefore, a total of 68 mL whole blood for cellular sampling and 8 mL serum for humoral sampling is required on Day 0 prior to 1st dose. Subjects may be asked to return for additional blood draws if collected blood sample is lost or unevaluable for any reason. Details of the immunology sample collection and shipment information will be provided in the Laboratory Manual.

Humoral samples will be collected on all subjects and cellular samples will be collected at selected sites (from approximately 711 subjects). Both humoral and cellular analysis will be conducted in the first 102 subjects age 18-50 and in the first 102 subjects age 51 and older enrolled at the sites that are selected for cellular sample collection. In addition, cellular and humoral samples will be analyzed on all subjects with COVID-19 when samples are available.

The immune responses to INO-4800 will be measured using assays that include a pseudovirus-based neutralization assay and ELISpot. Determination of additional analyses using assays not specified, such as assessment of immunological gene

Protocol Version: 2.0USA

expression or flow cytometry, assessment of immunological protein expression on collected samples for immunological endpoints will be made on an ongoing basis throughout the trial.

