- g. On Day 0, cellular sampling requires 64 mL of whole blood prior to 1st dose. At all other time points, collect 32 mL of whole blood. Cellular samples will be collected at selected clinical sites (estimated to include 711 subjects)
- h. On Day 0, humoral sampling requires a total of 17 mL of whole blood (two 10-mL red top serum collection tubes, each 8.5 mL of whole blood, to produce four serum aliquots of 2 mL each). At all other time points, collect 8.5 mL of whole blood in a single 10-mL red top serum collection tube to produce two serum aliquots of 2 mL each.
- i. SARS-CoV-2 antibody.
- j. The Day 0 RT-PCR results will not be required prior to dosing on that day.
- k. Day 42 visit must occur at least 10 days after Day 28 visit.
- I. Subjects will be evaluated during a "COVID-19 assessment visit" when acute COVID-19 is suspected. The assessment visit may be performed in the clinic, subject's vehicle, or at a home visit and should be completed within 3 days of symptom onset or within 3 days of a positive result of a SARS-CoV-2 test.
- m. For subjects with confirmed SARS-CoV-2 infection during the trial, a convalescent visit should be scheduled approximately 28 days after symptom onset, or in the absence of symptoms, the date of positive SARS-CoV-2 test. If acute symptoms are ongoing the site should follow up with the subject via phone call or unscheduled visit after symptom resolution or stabilization
- n. Vital signs to be performed at COVID-19 assessment and convalescent visits include temperature, respiration rate, heart rate and oxygen saturation.
- o. Genotyping may also be performed on sample(s) collected at the COVID-19 assessment visit.
- p. Diaries to be used at selected sites only (estimated to include 711 subjects).
- q. Diary should be reviewed at the 14-day post-dose phone call or visit and collected at the next in-office visit.
- r. When possible, cellular and humoral immunology samples will be collected. Cellular samples will be collected at selected sites only.

CONFIDENTIAL

INO-4800	COVID19-311
Inovio Pharmaceuticals, Inc.	Clinical Protocol

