Dose selection for evaluation of efficacy in the Phase 3 segment will be based on Week 6 immunogenicity data and Week 8 safety data from the Phase 2 segment. Group-level unblinded summaries and analyses of safety will be produced once the Week 8 phone call visit data are completed for all subjects in the Phase 2 segment. Group-level unblinded summaries and analyses of immunogenicity will be produced once the Week 6 visit data are completed for all subjects in the Phase 2 segment. Subject treatment assignments will be unblinded after Phase 2 subjects have reached the Week 30 visit.

Phase 3 Segment – Efficacy

In the Phase 3 segment, approximately 6714 seronegative and 402 seropositive subjects 18 years of age and older will be randomized at a 2:1 ratio to receive either active investigational product (INO-4800, 2.0mg) or placebo (placebo for INO-4800). Approximately half of seronegative subjects and approximately half of seropositive subjects will be 18-50 years of age, and the other half will be \geq 51 years of age as is operationally feasible. Also, approximately 711 subjects will be \geq 65 years of age, if operationally feasible.

Subjects will be randomized in a stratified manner according to (a) age category (18-50 years vs. ≥51 years) on Day 0, and (b) presence of or absence on Day 0 of any of the following underlying medical conditions that increase risk of severe COVID-19 disease, per CDC criteria [1], as listed below:

- Cancer
- Chronic kidney disease

INO-4800	COVID19-311
Inovio Pharmaceuticals, Inc.	Clinical Protocol

- Chronic lung diseases, including Chronic obstructive pulmonary disease (COPD), asthma (moderate-to-severe), interstitial lung disease, cystic fibrosis, pulmonary hypertension
- Neurologic conditions including stroke or cerebrovascular disease, that do not impact cognition
- Diabetes (type 1 or type 2)
- Hypertension
- Heart conditions, such as heart failure, coronary artery disease, or cardiomyopathies
- HIV infection (CD4 count >200 cells/mm3 or undetectable viral load)
- Liver disease
- Obesity (BMI ≥ 30 kg/m2)
- Sickle cell disease or thalassemia, or
- Smoking (current or former smoker).

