4.2.2 PHASE 3 SEGMENT

- Acute febrile illness with temperature ≥100.4°F (38.0°C) or acute onset of upper or lower respiratory tract symptoms (e.g., cough, shortness of breath, sore throat) on Day 0 prior to dosing;
- Positive serologic test for SARS-CoV-2 at Screening (after approximately 402 subjects positive for SARS-CoV-2 serologic test are randomized, this criterion will apply to all remaining subjects);
- c. Pregnant or breastfeeding, or intending to become pregnant or intending to father children starting from the Screening visit until the last dose;
- d. Positive urine pregnancy test during screening or immediately prior to dosing;
- e. Known history of uncontrolled HIV based on a CD4 count less than 200 cells/mm³ or a detectable viral load within 3 months prior to screening;
- f. Is currently participating or has participated in a study with an investigational product within 30 days prior to Day 0 (documented receipt of placebo in a previous trial would be permissible for trial eligibility);
- g. Previous or planned receipt of an investigational (including Emergency Use Authorization (EUA) or local equivalent authorization) or licensed vaccine for prevention or treatment of COVID-19, MERS or SARS (documented receipt of placebo in previous trial would be permissible for trial eligibility);
- h. Immunosuppression as a result of underlying illness or treatment including:
 - Primary immunodeficiencies (conditions including hypothyroidism, Hashimoto's thyroiditis and vitiligo are allowed);
 - Long term use (≥7 days) of oral or parenteral glucocorticoids at a dose of ≥20 mg/day of prednisone equivalent (use of inhaled, topical, nasal, otic, and ophthalmic corticosteroids are allowed) in the past 6 months;
 - Current or anticipated use of disease modifying doses of systemic anti-rheumatic drugs (e.g., azathioprine, cyclophosphamide, cyclosporine, methotrexate) and biologic disease modifying drugs such as TNF-α inhibitors (e.g., infliximab, adalimumab or etanercept) or others;
 - History of solid organ or bone marrow transplantation;
 - History of or current receipt of any other clinically significant immunosuppressive drugs
 - Diagnosis of an autoimmune disease that may jeopardize the safety of the subject or require therapy that would interfere with study assessments or endpoint evaluation, or otherwise impact the validity of the study results.

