8.5.2.2 Immunogenicity

Phase 3 Segment

Post-baseline increases from baseline in interferon- γ ELISpot response magnitudes will be compared between treatment groups using differences in medians and associated non-parametric 95% CIs.

Post-baseline increases from baseline in neutralizing antibody response titers will be compared between treatment groups using ratios of geometric mean fold-rises and associated t-distribution based 95% CIs.

The summaries listed above will be stratified according to disease status of the subjects and by baseline SARS-CoV-2 serostatus.

Valid samples for statistical analysis purposes will be those collected: at least 6 and no more than 30 days after Dose 2 for the Week 6 timepoint; at least 174 and no more than 198 days after Dose 2 for the Week 30 timepoint; and at least 356 and no more than 380 days after Dose 2 for the Week 56 timepoint. Baseline is defined as the last measurement prior to the first treatment administration.

The PP population will be used for these immunogenicity analyses.

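### The Phase 3 immunogenicity assay subset is filled by age and enrolment order alone, so no rule fixes how many seronegative or seropositive subjects it contains

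*Protocol*

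**What the plan says.** Section 6.5 (Immunogenicity Assessments) reads the same in the two full protocol versions at hand, 1.0USA and 2.0USA. Sera are taken from everyone, and "cellular samples will be collected at selected sites (from approximately 711 subjects"; footnote g of Table 4 agrees. The assays are run on a smaller set: humoral and cellular analysis "will be conducted in the first 102 subjects age 18-50 and in the first 102 subjects age 51 and older enrolled", limited to those "enrolled at the sites that are selected for cellular sample collection". Samples from all COVID-19 cases are assayed as well, where they exist. Serostatus is not mentioned in the selection rule.

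Three other provisions bear on this:

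- Section 4.2.2, criterion b, excludes a positive screening serology, but "after approximately 402 subjects positive for SARS-CoV-2 serologic test are randomized, this criterion will apply to all remaining subjects". Seropositive subjects are thus admissible from the start and barred once the cap is reached.
- Section 8.5.2.2 has the Phase 3 ELISpot and neutralising antibody summaries "stratified according to disease status of the subjects and by baseline SARS-CoV-2 serostatus", in the per-protocol population.
- Section 8.7 stratifies the 2:1 randomisation by age group and underlying conditions. Serostatus is not a factor.

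Section 3.0 plans for "approximately 6714 seronegative and 402 seropositive subjects".

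**The concern.** The subset is chosen without regard to serostatus and then reported by serostatus. The cap does not protect either stratum: 402 is larger than the whole subset of 204, and about 201 per age group is larger than 102. No floor or quota is stated.

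Two things are at stake. The seronegative stratum corresponds to the population in which primary efficacy is tested, and its size in the immunogenicity comparison is left to chance, with the placebo arm, at one third, the smaller side. The seropositive stratum is also reported separately and may be too small to show anything. A low seropositive share starves that stratum, and a high share takes subjects from the seronegative one.

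**Working it through.** **Inputs from the protocol.** Subset 102 + 102 = 204 (Section 6.5). Allocation 2:1 (Section 8.7), so 102 is 68:34 and 204 is 136:68 in expectation. Planned enrolment 6714 + 402 = 7116 (Table 2). Cellular-sample pool about 711 (Section 6.5; Table 4, footnote g). Age split of the seropositives: "Approximately half of seronegative subjects and approximately half of seropositive subjects will be 18-50 years of age", so about 201 per age group.

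**Not given.** The seropositive share among early enrollees, and when the cellular sites open relative to the cap. Both are assumptions below.

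**The plan's own figure.** The protocol gives no derivation, power or precision target for the 102s, so there is nothing to reproduce for the subset. The figure it does derive reproduces: 149 / (0.037 × (2 × 0.4 + 1)/3) = 149 / 0.0222 = 6712, against 6714 stated. It does not depend on the assay subset.

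**Step 1: trial-wide share.** 402 / 7116 = 5.6%. If the subset matched it, 204 × 0.0565 = 11.5 subjects would be seropositive, of whom 11.5 / 3 = 3.8, about 4, would be on placebo. The seronegatives would number about 192 (128:64), with interval width × √(204/192.5) = 1.03.

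**Step 2: what the cap implies under proportional enrolment.** The cellular sites hold 711 / 7116 = 10.0% of subjects. Their expected share of the 402 seropositives is 402 × 711 / 7116 = 40.2, or about 20 per age group. The subset is complete when about 204 / 0.0999 = 2042 subjects have been enrolled trial-wide. With a seropositive share s among early enrollees, the cap closes at 402 / s: after 4020 enrolled at 10%, 2010 at 20% and 1340 at 30%. The expected number of seropositives in the subset is therefore the smaller of 204s and 40.2:

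| s (assumed) | seropositive | seronegative (INO-4800:placebo) | interval width factor |
|---|---|---|---|
| 5.6% | 11.5 | 192 (128:64) | 1.03 |
| 10% | 20.4 | 184 (122:61) | 1.05 |
| 20% or more | about 40 | 164 (109:55) | 1.12 |

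The width factor is √(204 / number seronegative), relative to 204 seronegatives. Per age group, the last row is about 82 seronegatives, near 55:27.

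**Step 3: what that means for a titre ratio.** The protocol gives no standard deviation. Take the SD of log10 fold-rise as 0.5. The 95% interval for the ratio of geometric mean fold-rises within one age group is then the estimate multiplied and divided by 1.62 with 68:34 seronegatives, and by 1.71 at 20% seropositive. With an SD of 0.4 the change is from 1.47 to 1.54; with 0.6 it is from 1.78 to 1.91.

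**Step 4: departures from proportionality.** If the cellular sites open after the cap has filled, all 204 are seronegative and the seropositive stratum is empty. If they take more than their share of seropositives, the loss exceeds 40. Having 30% of the 204 seropositive would need about 61 seropositives, which is 15% of all 402 at sites with 10% of the subjects. The protocol neither rules this out nor suggests it.

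These are expected counts before the per-protocol restriction, which lowers them by an unknown amount.

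**The case against.** The case for leaving the text alone has substance. Secondary objective 3 is to evaluate the immune response to INO-4800 without limit to seronegatives, although objectives 2 and 4 each name a serostatus; a mixed subset reported by serostatus meets it as written. The endpoint is estimated, with no formal hypothesis (Section 8.3). Phase 2 already measures the same two assays in about 400 seronegative subjects, including 150 on 2.0 mg and 50 on two-injection placebo. Any shortfall can be made good from stored material. Section 6.5 of version 7.0, of which only the closing pages are at hand, may also differ.

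Most of this stands, and it limits the importance of the point. It does not supply a number for either stratum.

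A reader might infer more: that the subset is drawn exactly while seropositives are being admitted, that it must hold far more than 5.6% of them, and that it represents only the earliest sites and calendar period. The protocol does not support this. The rule is the first 102 per age group at the selected sites, and no opening order or seroprevalence is stated. A 60% seropositive subset, leaving 82 seronegatives of whom 27 are on placebo, would need about 122 of the 402 seropositives (30%) at sites holding 10% of subjects.

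**Conclusion.** The point holds as a gap in a stated rule. Section 6.5 fixes the subset by age and order of enrolment, Section 8.5.2.2 splits it by serostatus, and nothing fixes the size of either part.

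The likely size is modest. Under proportional enrolment at the cellular sites, up to about 40 of 204 seronegative places are lost, and intervals are up to about 1.12 times wider. A larger loss requires those sites to take a disproportionate share of the 402 seropositives. At the other end, a 5.6% share leaves about 4 seropositive placebo subjects, too few for a useful comparison.

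A reader might also infer bias in the immunogenicity comparison or damage to the efficacy result. Neither follows. Comparisons within serostatus remain randomised comparisons, and the primary test and its error rate do not use this subset. The cost is precision in a secondary endpoint, and the correction is cheap enough to be worth making.

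**What to change.** In Section 6.5, define the subset as the first 102 baseline-seronegative subjects in each age group at the cellular-sampling sites. This gives an expected 68:34 per age group and 136:68 overall, whatever the seroprevalence. Add a stated number of baseline-seropositive subjects per age group. For ELISpot that number has to be attainable from the cellular pool, which holds about 20 seropositives per age group under proportional enrolment. Keep the assay of all COVID-19 cases.

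No new blood draws are needed. The cost is the extra assays for the seropositive set and a slightly later completion of the subset: under proportional enrolment, at most about 204 + 40 = 244 subjects at those sites instead of 204, well inside the 711. Blinded random selection from the stored pool, by age group and serostatus, is an option if the sponsor also wants to avoid dependence on enrolment order. It would delay the assays further and is not needed to settle this point.

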7.0 EVALUATION OF SAFETY AND MANAGEMENT OF TOXICITY

7.1 SAFETY PARAMETERS

The safety of INO-4800 will be measured and graded in accordance with the Common Terminology Criteria for Adverse Events (CTCAE), version 5.0.

7.2 ADVERSE EVENTS (AES)

Any untoward medical occurrence in a patient or clinical investigation subject administered a pharmaceutical product and which does not necessarily have a causal relationship with this treatment.

An AE can therefore be any unfavorable and unintended sign (including an abnormal laboratory finding, for example), symptom, or disease temporally associated with the use of a medicinal product, whether or not considered related to the medicinal product.

Adverse Events (AEs) include the following:

- Pre- or post-treatment complications that occur as a result of protocol mandated procedure during or after screening (before the administration of clinical trial drug);
- Any pre-existing condition that increases in severity, or changes in nature during or as a consequence of the clinical trial drug administration phase;
- Complications of pregnancy (refer to Section 7.11).

Adverse Events (AEs) do not include the following:

- Medical or surgical procedures (e.g., surgery, endoscopy, tooth extraction, transfusion) performed; however, the condition that leads to the procedure is an AE;
- Pre-existing diseases or conditions or laboratory abnormalities present or detected before the Screening Visit that do not worsen;
- Situations where an untoward medical occurrence has not occurred (e.g., hospitalization for elective surgery, social and/or convenience admissions);
- Overdose without clinical sequelae;
- Any medical condition or clinically significant laboratory abnormality with an onset date before the ICF is signed, is not an AE; it is considered to be pre-existing and will be documented on the medical history CRF;
- Uncomplicated pregnancy;
- An induced elective abortion to terminate a pregnancy without medical reason;
- Confirmed COVID-19 disease.

